## 7.2 Method of Treatment Assignment

During the screening visit for all study parts, the investigative site will call into the enrollment option of the IRT designated by BMS for assignment of a 5-digit participant number that will be unique across all sites. Enrolled participants, including those not dosed, will be assigned sequential participant numbers starting with █. The participant identification number (PID) will ultimately be comprised of the site number and participant number. For example, the first participant screened (ie, enrolled) at site number 1, will have a PID of █. Specific instructions for using the IRT system will be provided to the investigational sites in a separate document.

Participants will not be replaced if they are discontinued from the study secondary to an AE unless the AE can be determined to be unrelated to treatment.

During dose escalation, all participants will be assigned to Part 1A until the decision is made to escalate to the third dose cohort. Subsequently, treatment in Part 1B will be initiated, and dose escalation in the 2 parts will occur in parallel. █ will be initiated once an appropriate BMS-986288 monotherapy or combination dose is identified, will be incorporated through a protocol amendment, and may run in parallel with Part 1A and Part 1B. Treatment assignments for participants eligible for Part 1A, Part 1B, or █ will alternate between the 3 parts (if open), with consecutively treated participants assigned to different parts through IRT whenever possible according to the corresponding inclusion criteria. If there are no openings available in the part to which the participant would be assigned by this algorithm, then the participant will be

assigned to the next open part/cohort. Prioritization of participants eligible for both Part 1A and Part 1B may be modified to ensure the dose of BMS-986288 in the Safety Evaluation of BMS-986288 in Combination with Nivolumab (Part 1B) does not exceed the highest dose evaluated in the BMS-986288 Monotherapy Dose Escalation (Part 1A).

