#### **7.4.1 Dose-limiting Toxicities**

For the purpose of guiding dose escalation, all AEs will be assessed and DLTs will be defined based on the incidence, intensity, and duration of the AEs for which no clear alternative cause is identified. The DLT period will be 5 weeks (35 days) in both BMS-986288 monotherapy and combination dose escalation (Part 1A and Part 1B). Any toxicities that occur beyond the DLT period will be accounted for in making final dose level decisions. Participants who have discontinued due to a DLT or who have received 2 doses of BMS-986288 monotherapy or in combination with nivolumab and have completed the 5-week DLT period will be considered as DLT-evaluable participants. Participants who withdraw from the study during the DLT evaluation period or have received less than 2 doses for reasons other than a DLT in both monotherapy and combination therapy will not be considered as DLT-evaluable participants and may be replaced with a new participant at the same dose level. Participants who are dose delayed during the DLT evaluation period for reasons other than a DLT in both monotherapy and combination therapy will be considered as DLT-evaluable participants if they received at least 2 doses of therapy within 8 weeks.

For the purpose of participant management, any drug related AE that meets DLT criteria, regardless of the cycle or cohort in which it occurs, will lead to discontinuation of study treatment.

AEs will be graded according to the NCI CTCAE v5.0.

Continuous evaluation of toxicity events in the [REDACTED] Evaluation of BMS-986288 [REDACTED] and BMS-986288 Cohort Expansion Combination Therapy (Part 2) will be performed. If at any time, the aggregate rate of treatment-related toxicities meeting DLT criteria in a BMS-986288 containing cohort exceeds 33% across patients treated in a cohort, the findings will be discussed with the Investigators and further enrollment may be interrupted. If a cohort is discontinued due to toxicity, a new cohort at a previously tested alternative dose level which was found to be safe in Part 1A or Part 1B may be considered based on the aggregate safety experience and in consultation and agreement between Investigators and Sponsor. An alternative dose or administration schedule may also be initiated in a specific [REDACTED] or Part 2 cohort upon

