**Table 7.4.3.1-1: Adverse Event Criteria for Delay, Resume, and Discontinue of Nivolumab and/or BMS-986288**

Drug-Related Adverse Event (AE) per CTCAE v5	Severity	Action Taken	Clarifications, Exceptions, and Resume Criteria
Gastrointestinal			
Colitis or Diarrhea	Grade 2	Delay dose	Dosing may resume when AE resolves to baseline. Grade 2 colitis > 5 days is a DLT.
	Grade 3	Permanently discontinue	
	Grade 4	Permanently discontinue	
Hematologic			
Anemia	Grade 4	Delay or permanently discontinue	For first occurrence: Delay dose until recovery. If event recurs, permanently discontinue. Dose delay during Cycle 1 is considered a DLT.
Hemolysis	Grade $\geq$ 3	Permanently discontinue	
Neutropenia	Grade 3	Delay dose	Delay dose until recovery; resume treatment when AE resolves to Grade $\leq$ 1 or baseline. Grade 3 with duration $\geq$ 7 days during Cycle 1 is considered a DLT; resume treatment once AE resolves, as described above.
	Grade 4 or febrile neutropenia	Delay or permanently discontinue	If duration $<$ 7 days, delay until recovery. If duration $\geq$ 7 days or for neutropenic fever of any duration, permanently discontinue. Dose delay during Cycle 1 is considered a DLT.
Thrombocytopenia	Grade 3 thrombocytopenia $>$ 7 days or associated with Grade $\geq$ 2 hemorrhage	Delay or permanently discontinue	If duration $\leq$ 7 days, delay until recovery. If duration $>$ 7 days or associated with clinically significant bleeding, permanently discontinue.
	Grade 4	Permanently discontinue	
Renal			
Serum Creatinine Increased	Grade 2 or 3	Delay dose	Dosing may resume when AE resolves to Grade $\leq$ 1 or baseline value.
	Grade 4	Permanently discontinue	
Pulmonary			
Pneumonitis	Grade 2	Delay dose	Dosing may resume after pneumonitis has resolved to $\leq$ Grade 1.

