**Table 7.4.3.1-1: Adverse Event Criteria for Delay, Resume, and Discontinue of Nivolumab and/or BMS-986288**

Drug-Related Adverse Event (AE) per CTCAE v5	Severity	Action Taken	Clarifications, Exceptions, and Resume Criteria
Other Clinical AE			
Pancreatitis: Amylase or Lipase increased	Grade 3 with symptoms	Delay dose	Note: Grade 3 increased amylase or lipase without signs or symptoms or radiographic evidence of pancreatitis does not require dose delay. Dosing may resume when patient becomes asymptomatic.
	Grade 4	Permanently discontinue	Grade 4 increased amylase or lipase without signs or symptoms or radiographic evidence of pancreatitis does not require permanent discontinue.
Uveitis, episcleritis, iritis, eye pain, or blurred vision	Grade 2	Delay dose	Dosing may resume with response to topical therapy (eye drops) and after resolution to Grade $\leq$ 1 or baseline. If patient requires oral steroids, then permanently discontinue study drug.
	Grade 3 or 4	Permanently discontinue	
Other Drug-related AE (not listed above)	Grade 2 non-skin AE, except fatigue	Delay dose	Dosing may resume when AE resolves to Grade $\leq$ 1 or baseline value.
	Grade 3 AE - First occurrence lasting $\leq$ 7 days	Delay dose	Dosing may resume when AE resolves to Grade $\leq$ 1 or baseline value.
	Grade 3 AE- First occurrence lasting $>$ 7 days	Permanently discontinue	
	Recurrence of Grade 3 AE of any duration	Permanently discontinue	Exception to permanent discontinue: Grade 3 fatigue $<$ 7 days in any cycle does not require permanent discontinue. Grade 3 tumor flare (defined as pain, irritation, or rash that localizes to sites of known or suspected tumor). Grade 3 fever not associated with hemodynamic compromise (eg, hypotension, clinical, or laboratory evidence of impaired end-organ perfusion). Grade 3 nausea, vomiting, or abdominal pain that returns to Grade 1 or baseline within 48 hours, either spontaneously or with medical intervention.
	Grade 4 or Life-threatening adverse reaction	Permanently discontinue	

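### The DLT-evaluability rule in Section 7.4.1 turns on why a participant stopped, not on whether a DLT occurred, so an observed DLT can be left out of the escalation model; its replacement wording also needs reconciling with Section 7.2

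*Combined protocol and SAP*

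**What the plan says.** Section 7.4.1 has two routes into the DLT-evaluable set: "Participants who have discontinued due to a DLT or who have received 2 doses of BMS-986288 monotherapy or in combination with nivolumab", the second route also requiring completion of the 5-week (35-day) period. The exclusion covers those who withdraw from the study in that period, and it says that those who "have received less than 2 doses for reasons other than a DLT in both monotherapy and combination therapy will not be considered as DLT-evaluable participants"; both groups may be replaced at the same dose level. A further sentence keeps participants whose dosing was delayed for reasons other than a DLT, provided they received at least 2 doses within 8 weeks.

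Section 7.4.1 also says that a drug-related AE meeting DLT criteria leads to discontinuation of treatment. Section 7.4.4 makes exceptions to this, including those in Table 7.4.3.1-1. That table states that Grade 3 neutropenia of at least "7 days during Cycle 1 is considered a DLT; resume treatment once AE resolves, as described above". Under other laboratory abnormalities it lists Grade 4 lymphopenia or leukopenia as not requiring discontinuation, and calls it a DLT if it lasts more than 7 days.

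On replacement, Section 7.2 says: "Participants will not be replaced if they are discontinued from the study secondary to an AE unless the AE can be determined to be unrelated" (the relation meant is to treatment).

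Sections 10.1.1 and 10.1.2 feed DLT information from the DLT period into the BLRM (Part 1A) and BLRM-copula (Part 1B). Escalation with overdose control caps the posterior probability of a DLT rate of 33% or more at 35%. Section 5.1.2.1 sets cohorts of about 3.

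**The concern.** The evaluable set is the denominator of the escalation model, and membership should not depend on how a participant with a DLT happened to leave. As worded, the early route requires the DLT to be the reason for stopping. Where the table lets treatment resume after a DLT, the event and the reason for stopping can come apart, and the event is then lost with the participant.

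Early exit is foreseen: the sentinel-participant text in Section 5.1.2 allows a fourth participant per cohort because of discontinuations, such as for disease progression, before day 35. With cohorts this small, one lost DLT can decide whether a dose passes the overdose criterion.

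The second matter is procedural. Sections 7.2 and 7.4.1 each state who may be replaced, use different criteria, and do not refer to each other.

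**Working it through.** **1. Sorting participants by the text of Section 7.4.1.** Take a participant with a Cycle 1 DLT after which the table allows dosing to resume.

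- Stops treatment because of the DLT: evaluable.
- Resumes, receives 2 doses and completes 35 days: evaluable.
- Withdraws from the study within 35 days for another reason: not evaluable, replaceable.
- Misses dose 2 because of, say, progression: fewer than 2 doses for a reason other than a DLT, so not evaluable and replaceable.
- Second dose delayed by the DLT itself, so that only one dose has been given at day 35: neither discontinued because of a DLT, nor excluded (the reason is a DLT), nor covered by the delay sentence (which is for non-DLT reasons). No class applies.

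In the third and fourth cases an observed DLT leaves the model input. In the fifth its status is undefined.

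**2. Checking the calculation against a figure in the plan.** Section 10.3.8.1 gives a Part 2 boundary of 16 of 40, using Beta(0.5, 0.5), a 33% reference rate and a posterior threshold of 0.80. With n DLTs in m participants the posterior is Beta(0.5 + n, 0.5 + m − n).

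- 16/40: Beta(16.5, 24.5), P(rate > 0.33) = 0.827, above 0.80.
- 15/40: Beta(15.5, 25.5), P = 0.731, below 0.80.

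The boundary of 16 reproduces. This checks the tool only; no stated figure depends on the Part 1 evaluability rule.

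**3. Effect of one lost DLT.** The BLRM prior is not given, so the BLRM cannot be reproduced. As an assumption, a single dose level is analysed with the same beta-binomial form under four priors. The table shows P(rate > 0.33), to be compared with the 0.35 cap.

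| Prior | 1/3 (DLT counted) | 0/3 (dropped, replaced by a participant without a DLT) | 0/2 (dropped, not replaced) |
|---|---|---|---|
| Beta(0.5, 0.5) | 0.536 | 0.106 | 0.177 |
| Beta(1, 1) | 0.599 | 0.202 | 0.301 |
| Beta(0.33, 0.67) | 0.456 | 0.059 | 0.102 |
| Beta(0.25, 0.75) | 0.418 | 0.040 | 0.072 |

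Counting the DLT puts the dose over the cap under all four priors; losing it puts the dose under, with or without a replacement. If the replacement has already been treated and everyone is counted, the data are 1/4: 0.394, 0.468, 0.325 and 0.293 in the same order. The reversal against 0/3 then holds under only two of the four priors.

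**4. Long-run size, under an assumed range.** If a fraction d of DLTs is dropped and replaced, a true rate p appears as p(1 − d)/(1 − pd). For p = 0.33:

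- d = 0.05: 0.3135/0.9835 = 0.319.
- d = 0.20: 0.264/0.934 = 0.283.

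The chance of at least 2 DLTs in 6 falls from 0.642 to 0.619 and 0.542 respectively. The documents give no value for d.

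**5. Participants who stop early for an AE that is not a DLT.** The model input is DLT yes or no, so these are non-events. With Beta(0.5, 0.5), excluding one leaves 1/3 (0.536), while keeping that person as a non-event gives 1/4 (0.394). Likewise 1/4 (0.394, over the cap) becomes 1/5 (0.285, under it) when one more non-event is kept. Exclusion therefore raises the modelled rate relative to retention.

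Against the rate that full observation would have shown, let a fraction q stop this way and let r be their DLT probability had they been followed. The modelled rate is (p − qr)/(1 − q). With p = 0.33 and an assumed q = 0.10, it is 0.367, 0.330, 0.300 and 0.256 for r = 0, 0.33, 0.6 and 1. Understatement requires r to exceed p.

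**The case against.** The strongest reply is that the lost-DLT case needs a chain of events: a DLT for which the table allows resumption, followed by withdrawal or a missed second dose for another reason, inside 35 days. Most DLTs force discontinuation and are captured. Section 10.1.1 shows no intention to discard an observed DLT and even allows later AEs meeting DLT criteria into the model. Dose decisions also weigh data from all treated participants (Sections 10.1.1 and 10.1.2), safety tables use the treated population (Section 10.3.2), and the Safety Management Team reviews signals at least monthly (Section 5.1.6). All of this stands and limits the practical harm. It does not repair the model input on which the 35% cap is evaluated.

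A second reply is that the Beta(0.5, 0.5) prior belongs to Part 2 monitoring, whereas the BLRM borrows ipilimumab and nivolumab data and pools across dose levels. That is correct; the figures are illustrative.

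On replacement, Section 7.4.1 is permissive and Section 7.2 restrictive, so a site could satisfy both by not replacing. Section 7.2 speaks of discontinuation from the study, which Sections 8.1 and 8.2 separate from stopping treatment. A reader might infer flatly opposite instructions; the text supports only an unreconciled overlap. Grade 2 uveitis shows the difficulty. The table says "If patient requires oral steroids, then permanently discontinue study drug" and does not label the event a DLT, but it also does not say that unlabelled rows are not DLTs, and Section 7.4.1 gives no closed list.

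**Conclusion.** The point holds in two parts. First, by its wording Section 7.4.1 can remove an observed DLT from the Part 1 escalation data, and leaves one type of participant unclassified. The case should be uncommon and its frequency cannot be derived from the documents. When it occurs in a cohort of 3, the loss moves the illustrative posterior from 0.536 to 0.106 across the 0.35 cap, and the crossing held under all four priors tried. This rests on a single-dose beta-binomial in place of the BLRM. Part 2 is unaffected, because Section 10.3.8.1 treats every treated participant as evaluable.

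Second, Sections 7.2 and 7.4.1 overlap on replacement without being reconciled.

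A reader might go further and infer that excluding participants who stop for drug-related AEs short of a DLT also makes the model see too little toxicity. The documents do not support that. Removing a non-event raises the observed rate, and understatement would need early stoppers to be at higher DLT risk than the rest, which is plausible but not shown.

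This is a wording correction worth making to a stated rule, not a flaw that undermines the escalation design.

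**What to change.** In Section 7.4.1, replace the condition of having discontinued because of a DLT with *experienced a DLT during the DLT period*, and state that this makes the participant evaluable whatever the number of doses received or the reason for leaving. That covers both the dropped and the unclassified cases.

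Write one replacement rule and use it in Sections 7.2 and 7.4.1, saying whether it applies to discontinuation of treatment, of the study, or both. Do not settle the overlap by retaining participants who stop for a non-DLT AE in the evaluable set as non-events, since that can lower the modelled DLT rate and take a dose from over the cap to under it.

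The cost is a few sentences and no additional participants. The consequence to accept is that a dose may occasionally fail the overdose criterion where the present wording would have let it pass.

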#### **7.4.2 Management Algorithms for Immuno-oncology Agents**

I-O agents are associated with imAEs that can differ in severity and duration from AEs caused by other therapeutic classes. BMS-986288 and nivolumab are considered I-O agents in this protocol. Early recognition and management of imAEs associated with I-O agents may mitigate severe toxicity. Management algorithms have been developed from extensive experience with ipilimumab and nivolumab to assist Investigators in assessing and managing the following groups of imAEs:

- GI
- Renal
- Pulmonary
- Hepatic
- Endocrinopathies
- Skin
- Neurological (including encephalitis)
- Cardiac

The clinical nature of AEs noted with BMS-986288 will determine the role of the algorithms for use in toxicities related to its use in this study. The algorithms recommended for the management of imAEs in this protocol are in [Appendix 6](#).

#### **7.4.3 Dose Delays Due to Toxicity**

If an event is attributed to BMS-986288 or nivolumab, alone or in combination, then all study drugs must be delayed until treatment can resume (see [Section 7.4.3.1](#)). Delay administration of both nivolumab and BMS-986288 if any of the delay criteria in [Table 7.4.3.1-1](#) are met. Tumor assessments for all participants should continue per protocol even if dosing is delayed.

Participants who experience the following must have all study treatment(s) withheld:

- Potential DLTs, until DLT relatedness is defined.
- Drug-related select AEs and laboratory abnormalities in Table 7.4.3.1-1.
- AE, laboratory abnormality, or concurrent illness that, in the judgment of the Investigator, warrants delaying study treatment administration.
- Confirmed SARS-CoV-2 infection.

Participants who require a delay of study drug should be re-evaluated weekly or more frequently if clinically indicated. For participants receiving a combination (eg, Part 1B, [REDACTED], Part 2B), if dosing is delayed, then study drugs must be delayed together. If dosing with both study drugs is to be resumed after a delay, then both must be resumed on the same day. Criteria for participants who are required to permanently discontinue study treatments are listed in [Section 8.2](#). In addition,

all AEs should be evaluated and managed per the toxicity management algorithms in [Appendix 6](#). Participants not meeting guidelines for permanent discontinuation will be permitted to resume therapy based on the criteria specified below in Section 7.4.3.1. Participants eligible to resume study therapy will resume study therapy at the nominal treatment visit after their last received study medication dose.

#### **7.4.3.1 Criteria to Resume Treatment**

Subsequent dosing with study therapy may resume once drug-related non-DLT AEs resolve to Grade 1 or baseline. When criteria to resume treatment are met, resume both nivolumab and BMS-986288 on the same day.

- Participants experiencing AEs not meeting criteria for permanent discontinuation may resume treatment with study intervention(s) if they have completed AE management (eg, corticosteroid taper) or are on  $\leq$  10 mg prednisone or equivalent and meet the requirements per [Table 7.4.3.1-1](#).
- Prior to re-initiating treatment in a participant with a dosing delay lasting  $>$  8 weeks (unless the exceptions in [Table 7.4.3.1-1](#) are met), the Medical Monitor (or designee) must be consulted. Continue tumor assessments per protocol even if dosing is delayed. Continue periodic study visits to assess safety and laboratory studies [REDACTED] or more frequently if clinically indicated during such dosing delays.
- Participants with confirmed SARS-CoV-2 infection may resume treatment after 1) at least 10 days (20 days for severe/critical illness) have passed since symptoms first appeared, positive RT-PCR test result, or positive viral antigen test result, 2) resolution of acute symptoms (including at least 24 hours has passed since last fever without fever reducing medications), 3) evaluation by the Investigator with confirmation that there are no sequelae that would place the participant at a higher risk of receiving investigational treatment, and 4) consultation by the medical monitor. For suspected cases, treatment may also resume if SARS-CoV-2 infection is ruled-out and other criteria to resume treatment are met.
  - Prior to re-initiating on-study treatment in a participant with a dosing delay lasting  $>$  8 weeks due to SARS-CoV-2 infection, the medical monitor/designee must be consulted.

**Table 7.4.3.1-1: Adverse Event Criteria for Delay, Resume, and Discontinue of Nivolumab and/or BMS-986288**

Drug-Related Adverse Event (AE) per CTCAE v5	Severity	Action Taken	Clarifications, Exceptions, and Resume Criteria
Gastrointestinal			
Colitis or Diarrhea	Grade 2	Delay dose	Dosing may resume when AE resolves to baseline. Grade 2 colitis > 5 days is a DLT.
	Grade 3	Permanently discontinue	
	Grade 4	Permanently discontinue	
Hematologic			
Anemia	Grade 4	Delay or permanently discontinue	For first occurrence: Delay dose until recovery. If event recurs, permanently discontinue. Dose delay during Cycle 1 is considered a DLT.
Hemolysis	Grade $\geq$ 3	Permanently discontinue	
Neutropenia	Grade 3	Delay dose	Delay dose until recovery; resume treatment when AE resolves to Grade $\leq$ 1 or baseline. Grade 3 with duration $\geq$ 7 days during Cycle 1 is considered a DLT; resume treatment once AE resolves, as described above.
	Grade 4 or febrile neutropenia	Delay or permanently discontinue	If duration $<$ 7 days, delay until recovery. If duration $\geq$ 7 days or for neutropenic fever of any duration, permanently discontinue. Dose delay during Cycle 1 is considered a DLT.
Thrombocytopenia	Grade 3 thrombocytopenia $>$ 7 days or associated with Grade $\geq$ 2 hemorrhage	Delay or permanently discontinue	If duration $\leq$ 7 days, delay until recovery. If duration $>$ 7 days or associated with clinically significant bleeding, permanently discontinue.
	Grade 4	Permanently discontinue	
Renal			
Serum Creatinine Increased	Grade 2 or 3	Delay dose	Dosing may resume when AE resolves to Grade $\leq$ 1 or baseline value.
	Grade 4	Permanently discontinue	
Pulmonary			
Pneumonitis	Grade 2	Delay dose	Dosing may resume after pneumonitis has resolved to $\leq$ Grade 1.

